- 3) The physician’s determination of the participant’s developmental age (for participants 7 years of age or older)
- 4) Feedback provided by any of the providers regarding the project

Determining Developmental Age

Since participants who are developmentally age 7 years or older¹ are asked by the SC to provide assent to participate in intervention 2 of the NCGENES study, the RA and SC must collect the developmental age of any child participant chronologically age 7 or older at the time of their first visit. Developmental age *must be collected* before the family is consented to study intervention 2 (i.e. genomic sequencing).

It is up to the RA to collect the developmental age of relevant participants. When the RA confirms the Visit 1 Appointment and Provider in the tracking system, a “Collect Developmental Age” task will appear for any participant 7 years or older chronologically. This indicates that a developmental age should be collected for this participant. The RA will need to consult with the provider after the visit to collect the developmental age of the child from them. The RA should record this developmental age by completing the “**Collect Developmental Age**” task in the tracking system (see page 146) and by making a note of the participant’s developmental age in the participant’s folder. If the participant is over 7 developmentally, the tracking system will automatically generate the required assent forms for the SC/GC to review with the participant. The SC/GC should also verbally confirm the developmental age with the RA.

¹ Pediatric participants in NCGENES 2 must be <16 years at eligibility determination. The age-specific study documents sent to parent participants are based on the age determined at eligibility. Pediatric participants may age-up while actively in the study, but age is treated as static in the study. Assent is based on the child’s *developmental* age at Visit 1.

Developmental age not available? If the provider does not inform the RA of a child's developmental age, the RA should ask the counselor (for genetics patients) or [name] (for neurology patients) if the provider has given them this information. If not, the RA should ask the counselor/[name] if the doctor can be reached so that the developmental age can be obtained. The RA should inform the person obtaining consent for study intervention 2 of the above ASAP.

The person obtaining consent for study intervention 2 will inform the parent of the following:

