If the participant signs assent form 1, they are told if they are in the group of kids that are asked to give a little bit of their blood (about 1-2 teaspoons) or if they are in the group of kids that do not have to do anything extra then what the doctor has already talked to their parent(s) about during their doctor's visit. The participant is asked if they have any questions, and if so, the questions are answered. Then depending upon the intervention 2 assignment the SC proceeds with assent 2 or with providing child and parent compensation as described [below](#).

Note: parent(s) are given a copy of the assent forms that are discussed with their child.

If the participant declines signing assent form 1, the SC informs the parent(s) and participant that study participation for intervention 2 cannot proceed. In the tracking system, the SC should exit (without saving) the current task and mark the participant "Refused" manually with the reason "Declined at Visit 1 – Intervention 2" and a short explanation.¹ Then the SC thanks the family for their time, provides parent and child compensation as described below, and escorts them to either phlebotomy (for provider bloodwork), check-out, or towards the appropriate hospital exit.

If the participant declines assent form 2, the SC informs the participant that no genetic sequencing will be done but the participant would continue to be in the NCGENES 2 study and the parent would be provided with follow-up surveys. Then the SC thanks the family for their time, provides parent and child compensation as described below, and escorts them to either phlebotomy (for provider bloodwork) or check-out, or towards the appropriate hospital exit. These participants will have a status of "Declined Consent/Assent to GS"

¹ See page 18 for more information on marking participants refused.

Cases of discordant consent/assent. If a child can assent to participate in Intervention 2, both the parent and child must agree to continue participation. Further, both parent and child must have concordant consent/assent for the check boxes related to the study's continued access to the child's medical records and for the disclosure of medically actionable secondary findings. If the child is 7 years or older chronologically and developmentally, the parent must consent AND the Child must assent for the participants (parent-child pair) to remain in NCGENES.

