If the consent and assent are discordant, a participant should be manually given the final status of REFUSED and a note detailing the reason for this change should be added to the participant's log in the study's tracking system.

Distribution of Parent and Child Compensation

At the completion of the consent/assent process parents will sign for compensation through the "Visit 1-Parent Reimbursement" task. For detailed instructions on this task see the "[Tracking System Tasks](#)" section on page 152. If the tracking system does not work, the SC will use a receipt book to complete this task. The study coordinator fills in the amount provided to the parent according to what was completed before and during visit 1. Child participants in the study will be offered a nonmonetary gift at the end of visit 1. For more information on participant compensation, see the "[Tracking Participant Compensation](#)" section on page 35.

Biospecimen collection

After the appropriate forms are signed (i.e. parental consent form 2 and if necessary, assent form 2) and the parent and child compensation have been distributed, the SC escorts the family to the phlebotomy area appropriate to that clinic. At UNC, the SC will direct the participants to UNC's Women's Hospital for phlebotomy check-in. If the patient is having provider bloodwork, the SC escorts the parent to the individual check-in area. If the patient is not having provider bloodwork, the SC escorts the family to the area where they can pull a number for general check-in. At Mission, the SC will direct the family to the phlebotomy area of the Mission Children's Hospital.

When the participant is called for blood draw, the SC should escort the family to the blood draw area and inform the phlebotomist of the need to use the research blood tubes immediately after the provider's blood order is filled. The SC will pass the phlebotomist the labeled research blood tube either right before they are to be filled or places them next to the tubes for the provider's bloodwork, depending upon the level of SC assistance needed.

SC assistance

When necessary, the SC assists the phlebotomist/parent in holding the child for blood draw, as well as trying to keep them calm for this procedure. Assistance is typically needed, however the SC should take care not to obstruct the phlebotomist.

See biospecimen protocol regarding sample labeling, collection, lab distribution, processing, and reporting.

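### The protocol gives two incompatible outcomes for a child who declines sequencing assent (form 2); coding it REFUSED would remove randomised families from the GS arm only

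*Protocol*

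**What the plan says.** In the Visit 1 part of the protocol, under Obtaining assent, a child with a developmental age of 7 or more is asked for two assents: form 1 for randomisation and form 2 for sequencing. Form 2 arises only after assignment to GS: "Then depending upon the intervention 2 assignment the SC proceeds with assent 2 or with providing child and parent compensation".

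Two rules then bear on a child who says no to form 2.

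- **Specific rule (child declines assent form 2).** The child is told that "no genetic sequencing will be done but the participant would continue to be in the NCGENES 2 study". The parent goes on receiving follow-up surveys, and the status is Declined Consent/Assent to GS.
- **General rule (the note on cases of discordant consent/assent, which follows).** It opens with "If a child can assent to participate in Intervention 2, both the parent and child must agree to continue participation". It also requires parent and child to tick the same way on two boxes, one for medical-record access and one for secondary findings. It then says that "the parent must consent AND the Child must assent for the participants (parent-child pair) to remain in NCGENES", and closes with "If the consent and assent are discordant, a participant should be manually given the final status of REFUSED".

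Appendix III (item 5c) states that the analysis will be by intention to treat.

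**The concern.** The two rules send the same randomised family in opposite directions. One keeps the family in survey follow-up. The other gives a manually entered final status, which only tracking-system administrators can change (footnote on manual statuses under Participant Eligibility). Two coordinators, or two sites, could follow the protocol and code identical families differently.

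What is at stake is comparability of the arms. A refusal at form 2 happens after assignment and can happen only in GS. If such families are coded REFUSED and follow-up stops, GS outcomes come from pairs who agreed with each other about sequencing, while No GS outcomes come from all pairs. Randomisation does not protect that comparison.

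**Working it through.** No figure in the protocol is being tested, so the check is mainly a comparison of text.

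**Step 1. Does the general rule reach form 2?** Its opening condition is assent to Intervention 2. Determining Developmental Age glosses the term when it speaks of the family being "consented to study intervention 2 (i.e. genomic sequencing"). Obtaining assent introduces forms 1 and 2 together and makes assent a condition of continuing. It adds that assent is usually taken once the parent's consent process is complete. In that order, a child who declines form 2 after the parent has signed consent form 2 is discordant by definition. As written, the rule reaches the case.

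**Step 2. Which outcome does the rest of the protocol fit?**

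| Place | Event | Outcome |
|---|---|---|
| Study Intervention 2 and Phone Consent to Intervention 2, If the Parent Declines | parent declines consent form 2 | follow-up continues; Declined Consent/Assent to GS |
| After Visit 1: All Participant Groups, footnote | randomised to GS but declines it | stays in, handled with No GS for return-of-results procedures |
| Genome Sequencing Assent task | child does not assent | task completed with a Declined button |
| Appendix IV, Consent form 1, item 6 | family decides against testing | interviews still take place |
| Appendix VIII, saliva letter | no saliva sample sent | surveys can continue |
| Note on discordant consent/assent | parent and child disagree | final status REFUSED |

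Retention is the pattern. REFUSED at form 2 is the exception.

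**Step 3. Which arm loses families?**

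- Form 1: every child needing assent is asked, in either arm. Discordance can remove families from both arms.
- Medical-record box: Appendix IV (Consent form 1, item 3) applies record follow-up whether or not GS is assigned. Both arms again.
- Form 2: GS only.
- Secondary-findings box: Appendix IV discusses this choice under Informed consent 2, so it appears to be GS only. Most of the consent and assent form screens are not in the copy reviewed, so the position of the boxes is inferred.

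**Step 4. Illustrative size.** Families affected at form 2 = (GS arm size) × a × d, where a is the share of children needing assent and d the share of those declining form 2. The protocol gives neither, so both are assumed. The Overview gives planned enrolment of 850, with 800 used in its diagram, and Appendix III gives 1:1 allocation: 850 / 2 = 425 and 800 / 2 = 400. Both are upper bounds, because enrolment precedes losses before the second randomisation.

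- Low: 425 × 0.20 × 0.05 = 4.25, or 1% of the arm.
- Middle: 400 × 0.40 × 0.05 = 8 to 400 × 0.40 × 0.10 = 16, or 2–4%.
- High: 425 × 0.50 × 0.20 = 42.5, or 10%.

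The corresponding No GS number is 0 in every row. If form 2 refusals are coded Declined Consent/Assent to GS, it is 0 in both arms.

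**The case against.** The best answer is that the protocol has already decided this exact case. It names the event, states the outcome, has a status whose label includes the word Assent, and provides a Declined button in the task. A form 1 refusal is handled quite differently: leave the task unsaved and mark Refused by hand. A specific rule would normally prevail over a general paragraph, and the general one could be read as meant for form 1 and the check boxes only.

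Much of that stands. It shows which outcome was probably intended and makes widespread miscoding less likely; nothing in the protocol shows that any family was coded REFUSED on form 2. But the discordance note does not state the narrower scope, and it comes after the specific rule, so staff have no instruction on which to follow. The narrower reading also has an odd result: a child who refuses the whole test stays in, while a pair who differ only on the secondary-findings box is removed.

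Two further cautions are fair. First, the assumed assent share may be too high, since assent depends on developmental age and the eligible conditions include intellectual disability and developmental delay. Second, REFUSED is a tracking status. Where the protocol means data to leave the analytic database, as for families found ineligible after enrolment, it says so, and it says nothing of that kind for REFUSED. The direct effect would be missing follow-up.

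**Conclusion.** The contradiction is real and worth correcting. For form 2 matters, REFUSED coding would be a one-arm loss after assignment, contrary to the stated intention-to-treat aim. The size is unknown. The 1–10% range rests on assumed assent and refusal rates and on arm sizes that are upper bounds; the contradiction depends on none of these.

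A reader might infer that the REFUSED rule as a whole ends follow-up in the GS arm only. The documents do not support that: the rule also covers form 1 and the medical-record box, which concern both arms. A reader might also infer that the protocol abandons intention to treat or treats a child's refusal more harshly than a parent's. Neither follows. Appendix III commits to intention to treat, and the specific rules give both refusals the same status with follow-up continuing. The problem arises only if the general note is allowed to override them.

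**What to change.** Reconcile the two passages in the discordance note:

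1. State that refusal of form 2 by parent or child means no sequencing, status Declined Consent/Assent to GS, surveys continuing, and analysis in the assigned GS arm. Grouping decliners with No GS for return-of-results logistics should not become their analysis group.
2. Keep REFUSED for discordance on form 1.
3. State how discordance on each check box is coded. Keep the concordance requirement for disclosing secondary findings, but do not let a mismatch on that box by itself end survey follow-up in the GS arm.
4. Audit REFUSED records for cases resting on form 2 alone. Correct the status only where form 1 consent, any required form 1 assent and the HIPAA authorisation were signed and the family has not asked to leave.

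The cost is a few sentences with ethics approval and a short record review. A child's refusal of sequencing is still fully honoured.

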- Pre-clinic visit 1 parent survey:

¹ The appointment does not need to occur within 30 days; it must be rescheduled within 30 days.

- **Question 6, A-G** (GAD7, anxiety, 7 items)
 - **Question 6, H-O** (PHQ8, depression, 8 items)
- Post-Return of results (2 weeks after RoR) parent survey:
 - **Question 21*, A-G** (GAD7, anxiety, 7 items)
 - **Question 21*, H-O** (PHQ8, depression, 8 items)
- Final Follow up (6 months after RoR) parent survey:
 - **Question 14*, A-G** (GAD7, anxiety, 7 items)
 - **Question 14*, H-O** (PHQ8, depression, 8 items)

*Question numbers subject to change

Both the GAD7 and the PHQ8 should be scored (separately) as follows:

- Not at all=0, Several days=1, More than half the days=2, Nearly every day=3
- Sum the items to create measure score
- If a participant scores 15 to 21 on the GAD7 (indicating severe symptoms) AND/OR scores 20 to 24 on the PHQ8 (indicating severe symptoms), the system will create an alert.

IMPORTANT NOTE: For any surveys administered by paper or over the phone, the data should be entered directly into the electronic data collection system within 24 hours of collection or first thing Monday morning if the data is collected late on Friday afternoon. Expedient data entry will allow for rapid distress score calculation, alert reporting, and appropriate follow-up action according to the protocol described above.

Immediately upon data entry, the tracking system will score each measure. If scores meet the thresholds specified above, the system will automatically send an email alert to the study coordinator and study clinical project director, notifying them of the participant's alert status and distress score(s). The system will also generate the "Parental Distress Follow-up" task to appear in the participant's individual page in the tracking system.

The clinical project director will:

1. Share this information with the study coordinator within 24 hours of email receipt.

The study coordinator will:

1. Complete the "Parental Distress Follow-up" task by selecting the "Get Started" button.

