If the parent completes the Pre-Visit 1 Questionnaire on paper, it should be entered into the tracking system within 24 hours. The survey must be scanned and uploaded as well as entered via the task.¹

[figure not shown]
1. First, upload a scan of the paper questionnaire to the **participant documents** page and label it “Pre-Visit 1 Parent Questionnaire _ID#”
2. From the individual participant’s page, click “Get Started” next to the Pre-Visit 1 Parent Questionnaire task, as shown below.

13 09/11/2019 Post-Visit 1 Clinician Questionnaire ver3 (2893) Pending  Get Started

3. The following pages will appear in succession. After entering the parent’s answers at each page, click the blue “Next” and repeat for subsequent pages. When all data is entered, click the blue “Finish & Finalize” button to complete the task (See [Page 11](#)).

[Page 1](#)

- Pre-Clinic Visit 1 Survey - Study Materials View Data

Instructions

Thank you for taking the time to participate in NCGENES. Please answer the questions on this survey. We are interested in learning about your experience, so we can find ways to provide better information and support to caregivers like you. You can skip any question that you are not comfortable answering.

We are committed to protecting your privacy. We will not share your responses to this survey with anyone outside of the study team.

Thank you again for participating in the study. Please do not leave after your child’s appointment until a study coordinator follows up with you.

Study Materials

Please check one box for the question below:

1. You were sent written materials about the NCGENES study before this appointment. How much of these materials did you read?

None A little bit Half Most All

Page 1 of 11

Next Save Save & exit

¹ If you encounter any ambiguity in an answer to one of the survey questions that requires interpretation, please consult with the Clinical Study Director, [name], by emailing her at [contact].

- Pre-Clinic Visit 1 Survey - Getting Information View Data

Getting Information

2. How confident are you in doing these things? Please tell us how confident you feel in doing each of the things listed below by selecting a number from 0 (not at all confident) to 4 (very confident). If you are not sure, choose the answer that is the best fit for how you feel.

I feel confident that I can:

A. Get the facts about my child's condition	Not at all confident	0	1	2	3	4	Very confident

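### The distress alert uses a plain item sum, yet parents may skip questions and no rule covers blanks, so an incomplete GAD7 or PHQ8 can fail to alert

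*Protocol*

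**What the plan says.** The section on the alert protocol for distressed adult participants lists two scales ("GAD7, anxiety, 7 items" and "PHQ8, depression, 8 items") on the pre-visit, 2-week and 6-month parent surveys. Items are coded "Not at all=0, Several days=1, More than half the days=2, Nearly every day=3", and the scoring instruction is "Sum the items to create measure score". The GAD7 range that triggers an alert is 15 to 21. For the PHQ8, a parent who "scores 20 to 24 on the PHQ8 (indicating severe symptoms), the system will create an alert". The two conditions are joined by and/or.

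The process is automatic: "Immediately upon data entry, the tracking system will score each measure". When a threshold is met, the system emails the study coordinator and the clinical project director and creates a follow-up task, which leads to the study psychologist.

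Page 1 of the Pre-Visit 1 Parent Questionnaire, reproduced in the tracking-system task guide, tells the parent: "You can skip any question that you are not comfortable answering". The 15 GAD7 and PHQ8 items come three pages later. The protocol has no proration, no minimum number of answered items, no required-response setting for these items and no check of individual items. In clinic, the research assistant only confirms that the survey shows as completed.

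**The concern.** The cut-offs are fixed totals that presume every item is answered, while the survey gives parents an open invitation to leave items out. The two instructions do not fit together. Under a plain sum, an omitted item lowers the ceiling of the total but not the bar it must clear.

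The failure would be silent: a sub-threshold or absent score produces no email, no task and no record that a scale was incomplete. The alert is the only score-based route to the psychologist. The protocol also states that no survey item asks about suicidality and that one goal of screening highly distressed parents is to find out whether ideation is present.

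**Working it through.** **Inputs**, all from the alert section: maximum 3 per item; 7 GAD7 items and 8 PHQ8 items; lowest alerting totals 15 and 20.

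**Reproducing the plan's figures.** Full-scale maximum = 3 × items: GAD7 3 × 7 = 21, PHQ8 3 × 8 = 24. These equal the upper ends of the printed alert ranges, so the ranges assume complete scales.

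**Case A: a blank adds nothing.** Maximum = 3 × (items − skipped). Mean needed per answered item = cut-off ÷ (items − skipped).

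| Skipped | GAD7 maximum (alert at 15) | Mean needed | PHQ8 maximum (alert at 20) | Mean needed |
|---|---|---|---|---|
| 0 | 21 | 2.14 | 24 | 2.50 |
| 1 | 18 | 2.50 | 21 | 2.86 |
| 2 | 15 | 3.00 | 18, impossible | 3.33 |
| 3 | 12, impossible | 3.75 | 15, impossible | 4.00 |

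With two GAD7 items skipped, an alert is possible only if all five remaining answers are at the maximum.

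**One PHQ8 item skipped.** The recorded total is the true total minus the value of the skipped item, and the alert is lost when that falls below 20.
- True 20: 20 − 1 = 19, so it is lost if the skipped item was worth 1, 2 or 3.
- True 21: 21 − 1 = 20 alerts; 21 − 2 = 19 does not. Lost at 2 or 3.
- True 22: 22 − 2 = 20 alerts; 22 − 3 = 19 does not. Lost at 3.
- True 23 or 24: at worst 20 or 21, so the alert survives.

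**Case B: no score when any item is blank.** One skip blocks that scale's alert whatever the other answers.

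**Under proration** (mean of answered items × number of items in the scale). PHQ8 with two skipped: 15 × 8/6 = 20 alerts. GAD7 with three skipped: 9 × 7/4 = 15.75 alerts; 8 × 7/4 = 14 does not. The maxima return to 24 and 21.

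**The case against.** The strongest reply is that the failure is inferred. The protocol gives the usual rule for a complete scale and does not say that blanks count as zero; the software may already handle missing items. That is fair as to the code, which cannot be seen. But a proration or imputation rule would have to exist there without appearing in the protocol, and neither other behaviour avoids the problem. Forcing a response on the tablet would not settle it, because the 2-week and 6-month surveys are mailed on paper.

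Several limits stand:
- Either scale can raise an alert, so losing one scale's trigger does not mean the parent is missed. The scales are also given at three time points, and a suicide screening script is available for ideation signalled in other study contact.
- The skip invitation is shown only for the pre-visit survey. The later surveys are not reproduced; for them there is only general interviewer guidance in Appendix XLI.
- A reader might infer that the most distressed parents are the ones who leave sensitive items blank. That is plausible, but nothing in the protocol documents it.
- A reader might also infer that GAD7 and PHQ8 outcome scores are biased downward. The protocol defines this sum for the alert and sets no analysis score. Missing items in an outcome belong to the statistical analysis plan, which is not shown.
- Proration extrapolates: four PHQ8 answers totalling 10 become 10 × 8/4 = 20.

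**Conclusion.** The concern holds for the alert rule as written. If blanks add nothing, two skipped PHQ8 items or three skipped GAD7 items make that scale's alert impossible, and one skipped PHQ8 item can cancel it for true totals of 20 to 22. If a blank voids the score, one skip suffices. The conclusion rests on the protocol's silence about blanks and on the absence of an undisclosed missing-item rule in the tracking system.

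The number of parents affected cannot be estimated, because no skip rate is given. The documents support a gap in one scale's trigger. They do not show that severely distressed parents go undetected overall, and they say nothing about outcome bias.

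This is an operational rule applied in real time on data entry, so a later analysis convention would not repair it.

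**What to change.** In the alert section, add a rule for incomplete scales that applies to the alert only and leaves the sponsor's cut-offs as they are:
- When at least half the items are answered (four or more on either scale), score the mean of the answered items times 7 for the GAD7 or times 8 for the PHQ8, and compare that with the existing cut-off.
- When fewer than half are answered, send an incomplete-scale notice through the existing alert route, so that a person sees it.

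The handling of surveys already entered should be left to the sponsor. If the software already has a missing-item rule, it should be stated in the protocol and checked against the ceilings above.

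The cost is a formula change in the tracking system and one added notice. The downside is a number of extra alerts for the coordinator and psychologist, expected to be small but not quantifiable without a skip rate.
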